#### **Follow-up visits during treatment**

Typical information to be collected at follow-up visits include:

- Date of follow-up visit (DD/MM/YYYY)
- Study continued (yes/no), if no
  - please complete end of observation visit

IMPACT number 18016; BETAPREDICT; Version 1.0, 12 February 2015

- Smoking (current, past, never)
- Employment status (employed, retired, keeping house, student, seeking work, self-employed, other, not reported)
- Marital status (married/partnership, single)
- Concomitant diseases
- Concomitant medication
  - Trade name or INN
  - Start date (at least year)
  - Stop date or "continued"
  - Daily dose, if applicable
  - Indication
- Disease course
  - Number of further demyelinating events/relapses (enter 0 if no further event since last visit)
    - If number >0: date of onset (DD/MM/YYYY)/ongoing
- Specific MS history
  - BETACONNECTTM auto-injector device still used (yes/no)
    - If no, please tick: Betaferon® treatment (ongoing/prematurely discontinued/unknown)
    - If ongoing, please specify which way of injection is used
      - Manual injection, BETACOMFORT®, BETAJECT Comfort®, BETAJECT lite®, other
    - If prematurely discontinued
      - last date of Betaferon® injection (DD/MM/YYYY)
      - reason [adverse event (please complete AE page), lack of efficacy, pregnancy, patient's wish, choice of other treatment (please specify)]
- Treatment days with Betaferon® since last visit
  - Number of expected treatment days
  - Number of true treatment days
- Local skin reactions (yes/no)
  - If yes; please tick

- a) (redness, other discoloration, hematoma, induration, lipodystrophy/atrophy, necrosis)
- b) (mild, moderate, severe)
- Participation in the BETAPLUS® nurse support program (yes/no; if no, please specify termination date)
- Participation in the PTMS program (yes/no; if no, please specify termination date)
- Intake of vitamin D supplements (yes vs. no; if yes which dosage?)
- Intake of other nutrients or vitamins (yes vs. no)
- EDSS
- Patient QQ results available (yes/no), if yes
  - please send back
- SF-36 results available (yes/no), if yes
  - please send back
- CES-D results available (yes/no), if yes
  - please send back
- WEIMuS results available (yes/no), if yes
  - please send back
- SDMT results available (yes/no) [only follow-up visit 2], if yes
  - please send back
- CMSS results available (yes/no)\*, if yes
  - please send back
- MSSM-R results available (yes/no), if yes
  - please send back
- ISU-DYA results available (yes/no)\*, if yes
  - please send back
- Change of concomitant medication compared to last visit (yes/no), if yes
  - Please fill out Concomitant Medication page
- Did adverse events or device events occur since the last visit (yes/no), if yes: Please fill out Adverse Event Report/Device Event Report

\*only for patients participating in the PTMS program.

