As part of the study we also plan to evaluate whether the **P**sycho-educative **T**raining for patients with **MS** (PTMS) may affect treatment adherence among patients using Betaferon®. The PTMS program is group-based trainings program that has been developed in 2009 and has been advanced since. It aims at helping patients deal with their MS as well as supporting them in developing a positive perspective of their lives, despite suffering from a chronic condition. The key focuses of the program are adequately coping with the disease, self-motivation for the required therapy, and continuity of treatment to ensure compliance/adherence.

The PTMS has been developed by a group of collaborating neurologists and psychologists. We have identified six neurology clinics, specialized in the treatment of MS offering the program as part of their clinical routine.

During clinical routine, the MS nurse or the treating neurologist recommends participation in the PTMS program if there is indication for inadequate coping, incompliance or deficit in knowledge about the disease. In general this pertains to all newly diagnosed patients, but also for example to experienced patients with "needle fatigue". Interested patients with the confirmed diagnosis of MS will be evaluated by a group leader. Exclusion criteria are severe depression or severe cognitive impairment. Groups consist of six to ten patients. The 90 minute sessions will be held with one to two weeks between each session until a series of 10 sessions has been completed. Sessions are mostly led by an experienced psychologist or MS nurse; however, sessions three, four and nine will be led by a physician or social worker. The program comprises knowledge transfer, exchange of experiences, role play, discussions, and self-reflection via diary.

The endpoints pertaining to the evaluation of the PTMS program, coping mechanisms, and social support will only be evaluated in patients from the six centers offering the program.

Approximately 90% of Betaferon® patients in Germany participate in the BETAPLUS® nurse support program. Hence, a subgroup analysis among those patients—while feasible—may not yield additional information and is not planned.

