#### 8.2 Secondary objective(s)

Secondary objectives are to evaluate at each visit:

- Satisfaction with the BETACONNECTTM autoinjector,
- Injection site pain,
- Flu-like symptoms following Betaferon® application,
- Analgesic use prior to Betaferon® application,
- Intake of vitamin D, other vitamins, and nutrients,
- If adherence to Betaferon® treatment is associated with:
  - depression,
  - health related quality of life,
  - coping mechanisms\*,
  - self-management mechanisms,
  - social support\*,

- fatigue, and
- cognition.
- If adherence to Betaferon® treatment at 12 (24) months is associated with number of relapses at 12 (24) months.
- If adherence to Betaferon® treatment at 12 (24) months is associated with EDSS change at 12 (24) months.
- If adherence to Betaferon® treatment is associated with utilities of treatment (only baseline and final visit).
- With respect to the subgroup of patients participating in the PTMS program (participants from PTMS centers vs. participants from non-PTMS centers):
  - At each visit, if the PTMS program is associated with:
    - treatment adherence,
    - depression,
    - quality of life,
    - self-management mechanisms,
    - fatigue,
    - cognition.
- In the subgroup of patients participating in the PTMS program:
  - At each visit evaluation of:
    - social support,
    - coping behavior.

\*only for patients participating in the PTMS program.

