# 9.2.7 Visits

The investigator documents an initial visit, follow-up visits and a final visit for each patient in the case report form (CRF). Follow-up visits occur during routine practice, the study protocol does not define exact referral dates for those visits. However, documented visits should be approximately six months apart. The final visit is to be documented after approximately 24 months. The observation period for each patient is therefore approximately 24 months.

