# Enrollment / Initial visit

Once a patient is found eligible for inclusion, the investigator will inform the patient about the study. Where applicable, this will include discussing the consent form and asking the patient to read and - when agreeing to participate - sign the informed consent.

Typical information to be collected at the baseline visit includes:

- Date of visit
- Date of birth (at least year)
- Sex (female, male)
- Race / ethnicity (Caucasian, asian, black, other)
- Height (cm)
- Weight (kg)
- Smoking (current, past, never)
- Employment status (employed, retired, keeping house, student, seeking work, self-employed, other, not reported)
- Education level (elementary education, secondary education, college or university education, not reported)
- Marital status (married/partnership, single)
- Medical history
  - Concomitant diseases
  - Concomitant medication
    - Trade name or INN
    - Start date (at least year)
    - Stop date or "continued"
    - Daily dose, if applicable
    - Indication
- Intake of vitamin D supplements (yes vs. no; if yes which dosage?)
- Intake of other nutrients or vitamins (yes vs. no)

IMPACT number 18016; BETAPREDICT; Version 1.0, 12 February 2015

- Specific MS history
  - Date of first clinical event suggestive of MS (DD/MM/YYYY)
  - Date of initial diagnosis (DD/MM/YYY)
  - diagnostic criteria
    - o according to McDonald criteria
    - o according to Poser criteria (CDMS)
  - Number of further demyelinating events/relapses (number during past 2 years)
    - If number >0: date of onset (DD/MM/YYYY), ongoing
  - Concomitant diseases of special interest
    - Depression
    - o Anxiety
    - o Fatigue
  - Betaferon® administration record
    - Betaferon® treatment (ongoing/naive)
    - Date of first Betaferon® injection (DD/MM/YYYY)
  - Current application form for Betaferon® (prior to study)
    - Manual injection (yes/no)
    - Use of auto-injection device (yes/no)
      - If Yes, please tick (BETACONNECTTM, BETACOMFORT®, BETAJECT Comfort®, BETAJECT lite®, other)
  - Treatment days with Betaferon® during last month
    - Number of expected treatment days
    - Number of true treatment days
    - o N/A
  - Participation in the BETAPLUS® nurse support program (yes/no)
  - Participation in the PTMS program (yes/no)

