#### 9.7.5 Analysis of secondary outcome(s)

Descriptive statistics will be used to summarize data from questionnaire scales and scores as well as clinical data using mean ( $\pm$  SD), median, minimum, maximum for continuous variables, and category

counts and frequencies (percentages) for categorical variables. Concomitant diseases on the case report form correspond to MedDRA terms. Concomitant medication will be coded using WHO's drug dictionary. Data will be recorded at each of the visits which will enable us to acknowledge and evaluate changes over time.

We will perform analyses for data obtained at each of the scheduled visits.

We will use linear or logistic regression analysis (depending on the outcome scale) to evaluate the association between participation in the PTMS program and adherence to Betaferon® treatment as well as between participation in the PTMS program and depression, health related quality of life, self-management mechanisms, fatigue, and cognition at each visit as well as change of these variables over time.

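### PTMS exposure is recorded as current status at visits about six months apart, although the course lasts 9–18 weeks, and it is defined by centre in some sections and by participation in others

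*Protocol*

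**What the plan says.** **The course.** Section 7 describes a group programme: "The 90 minute sessions will be held with one to two weeks between each session until a series of 10 sessions has been completed".

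**The visits.** Section 9.2.7 says "documented visits should be approximately six months apart".

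**The exposure item.** The initial visit lists "Participation in the PTMS program (yes/no") with no dates. The follow-up and final visits list "Participation in the PTMS program (yes/no; if no, please specify termination date"). Neither the visit lists nor the variables table in 9.3 shows a start date, a completion flag, a session count or an item for a course taken before enrolment.

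**The comparison.** Section 8.2 describes the PTMS objective as "participants from PTMS centers vs. participants from non-PTMS centers", and the power statement in 9.5 also contrasts PTMS with non-PTMS centres. Section 9.7.5 instead models the "association between participation in the PTMS program and adherence" and further outcomes at each visit. Section 9.7.4 lists participation among the baseline predictors.

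**Coping and social support.** In the initial, follow-up and final visit lists, CMSS and ISU-DYA carry the footnote "only for patients participating in the PTMS program". Section 7 and the footnote to the 9.3 table extend them to all patients at centres offering the programme.

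**The concern.** Because a no answer asks for a termination date, no is the natural tick once participation has ended. A patient who starts at baseline and attends all ten sessions would then be no at follow-up visit 1 and at every later visit. Used as it stands in the each-visit models of 9.7.5, the tick would place patients with the full course in the comparator and leave mainly those still mid-course as exposed. A course finished before enrolment has no clear code at baseline, where 9.7.4 takes participation as a predictor.

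Two things are at stake: dilution of the PTMS contrast, and an objective whose exposed group depends on which section is followed. A third follows from the footnote. Read as current participation, it would end CMSS and ISU-DYA collection when the course ends, although 8.2 asks for both at each visit.

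**Working it through.** **1. Course length against visit spacing.** Ten sessions have 9 gaps of 1–2 weeks (Section 7): 9 × 1 = 9 weeks to 9 × 2 = 18 weeks. Visits are about 26 weeks apart (9.2.7). A patient in the course at one visit will normally have finished by the next. If starts are spread evenly over an interval (an assumption; the protocol gives no start pattern), the share of courses still running at the next visit is 9/26 = 35% to 18/26 = 69%. The share already finished is 65% to 31%.

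**2. The protocol's own power figure.** Inputs from 9.5: difference 7 points, SD 8 or 10, alpha 0.05 (taken as two-sided), t-test, four group-size pairs. Noncentral t with ncp = 7 / (SD × √(1/n1 + 1/n2)) gives:

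| Groups | SD 8 | SD 10 |
|---|---|---|
| 30 vs 100 | 98.7% | 91.6% |
| 30 vs 220 | 99.4% | 94.8% |
| 60 vs 190 | >99.9% | 99.7% |
| 90 vs 160 | >99.9% | >99.9% |

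The stated >90% is reproduced.

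**3. Illustration of raw yes/no coding.** Let f be the share of the n1 participants ticked no and counted in the comparator, with the termination date ignored.
- Moved: m = f × n1. Coded yes: a = n1 − m. Coded no: b = n2 + m.
- Expected difference: d = 7 × (1 − m/b).
- Comparator variance: 100 + 49 × (m/b) × (1 − m/b).
- Power = Φ(d / √(100/a + variance/b) − 1.96).

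Example, 60 vs 190 with f = 0.65: m = 39, a = 21, b = 229 and m/b = 0.170, so d = 5.81. The variance is 106.9, the SE is √(100/21 + 106.9/229) = 2.29, and power = Φ(2.54 − 1.96) = 72%.

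| Groups (SD 10) | f = 0 | f = 0.31 (18-week course) | f = 0.65 (9-week course) |
|---|---|---|---|
| 30 vs 100 | 91.6% | 76% | 44% |
| 30 vs 220 | 94.8% | 83% | 53% |
| 60 vs 190 | 99.7% | 96% | 72% |
| 90 vs 160 | >99.9% | 98% | 76% |

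The f = 0 column applies if completers are recovered from the termination date or if groups are formed by centre. All figures ignore missing data and clustering by centre, and treat the smaller group as the participants.

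**4. What the listed data can and cannot recover.**
- Never versus former participant during the study: recoverable, because a former participant has a termination date. This includes a course that starts and ends between two visits.
- Completed versus left early: not recoverable; both give no plus a date.
- Start of the course: not recorded, so the time since first exposure at a visit is unknown.
- A course before enrolment: not clearly coded at baseline.

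**The case against.** The strongest reply is that the termination date already solves the main problem. It separates former from never participants at follow-up, and nothing in the protocol tells the analyst to discard it. This stands: putting completers in the comparator is a risk of using the raw tick, not something the protocol prescribes.

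Second, the objective and the power statement group by centre, and the visit item cannot disturb that grouping. This also stands for a centre contrast. It does not settle 9.7.4 and 9.7.5, which use participation. Nor are the two the same: Section 7 says the programme is recommended on indication, taken up by interested patients and subject to exclusions.

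Third, calculated variables are left to the SAP, and the visit lists describe typical information, with the CRF a separate document. Choosing ever or current coding could indeed be an SAP matter. A later SAP cannot, however, supply a start date, completion status or earlier course that was never collected. That these are absent is read from the visit lists and the variables table, since the CRF itself is not shown.

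A reader might infer that the analysis compares the wrong groups and that the PTMS question cannot be answered, with power of about 22–40%. That range assumes 60 exposed of 250 and starts spread evenly over 104 weeks. Only 9/104 = 9% to 18/104 = 17% of courses would then still be running at the 24-month visit, so 5–10 patients would be coded yes. It needs the raw 24-month tick alone, the termination date ignored, no grouping by centre and that even spread. The protocol specifies none of these, so the range is not the study's expected power.

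**Conclusion.** The point holds as a defect of exposure definition and recording. The item reads as current status for a course shorter than the visit interval. The baseline item cannot place an earlier course. Completion and start date are not among the listed data. The exposure also switches between centre (8.2, 9.5) and participation (9.7.4, 9.7.5) without a time rule.

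The effect depends on a choice that the protocol leaves open. If the raw yes/no were used, with 31–65% of participants misplaced and SD 10, power would be about 44–98% across the protocol's group sizes. If the date is used, or groups are formed by centre, the stated >90% is unaffected. The misplaced shares rest on an assumed even spread of course starts and are illustrative. The inconsistent CMSS and ISU-DYA footnotes are a smaller, related fault. The change is a worthwhile, inexpensive improvement; the PTMS objective is not lost without it.

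**What to change.** - **Data.** Record PTMS start date, end date and whether the course was completed (or the number of sessions attended), including any course before enrolment.
- **Definition.** State one exposure in 9.7.4 and 9.7.5: ever started before the visit in question, with completed versus not completed as a secondary coding. Say that current status at the visit is not the exposure.
- **Consistency.** Reconcile this with the centre-based contrast in 8.2 and 9.5: say which is the main comparison, and attach the power statement to it.
- **Questionnaires.** Reconcile the CMSS and ISU-DYA footnotes in the three visit lists with Section 7 and the 9.3 table, so that collection does not stop when the course ends.

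The cost is a few eCRF fields, mainly at the six PTMS centres, one derivation rule and a small data-entry burden. Annex 1 lists the CRF as still to be issued, so the fields can be added before data collection.

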## **Final Visit and End of Observation period**

The final data collection (last visit) is after approximately 24 months, at discontinuation of therapy or at end of study (whatever is earlier). At this final observation point, the patient's condition and a treatment assessment will be documented, including:

- Date of follow-up visit (DD/MM/YYYY)
- Study continued (yes/no), if no
  - please complete end of observation visit
- Smoking (current, past, never)
- Employment status (employed, retired, keeping house, student, seeking work, self-employed, other, not reported)
- Marital status (married/partnership, single)
- Medical history
  - Concomitant diseases
  - Concomitant medication
    - Trade name or INN
    - Start date (at least year)
    - Stop date or "continued"
    - Daily dose, if applicable
    - Indication
- Disease course
  - Number of further demyelinating events/relapses (enter 0 if no further event since last visit)
    - If number >0: date of onset (DD/MM/YYY)/ongoing
- Specific MS history
  - BETACONNECTTM auto-injector device still used (yes/no)
    - If no, please tick: Betaferon® treatment (ongoing/prematurely discontinued/unknown)
    - If ongoing, please specify which way of injection is used
      - Manual injection, BETACOMFORT®, BETAJECT Comfort®, BETAJECT lite®, other
    - if prematurely discontinued
      - last date of Betaferon® injection (DD/MM/YYYY)

- reason [adverse event (please complete AE page), lack of efficacy, pregnancy, patient's wish, choice of other treatment (please specify)]
- Treatment days with Betaferon® since last visit
  - Number of expected treatment days
  - Number of true treatment days
- Local skin reactions (yes/no)
  - If yes; please tick
    - a) (redness, other discoloration, hematoma, induration, lipodystrophy/atrophy, necrosis)
    - b) (mild, moderate, severe)
- Participation in the BETAPLUS® nurse support program (yes/no; if no, please specify termination date)
- Participation in the PTMS program (yes/no; if no, please specify termination date)
- Intake of vitamin D supplements (yes vs. no; if yes which dosage?)
- Intake of other nutrients or vitamins (yes vs. no)
- EDSS
- Patient QQ results available (yes/no), if yes
  - please send back
- SF-36 results available (yes/no), if yes
  - please send back
- EQ-5D results available (yes/no), if yes
  - please send back
- CES-D results available (yes/no), if yes
  - please send back
- WEIMuS results available (yes/no), if yes
  - please send back
- SDMT results available (yes/no), if yes
  - please send back
- CMSS results available (yes/no)\*, if yes
  - please send back
- MSSM-R results available (yes/no), if yes

- please send back
- ISU-DYA results available (yes/no)\*, if yes
  - please send back
- Change of concomitant medication compared to last visit (yes/no), if yes
  - Please fill out Concomitant Medication page
- Did adverse events or device events occur since the last visit (yes/no), if yes: Please fill out Adverse Event Report/Device Event Report

\*only for patients participating in the PTMS program.

# 9.3 Variables

The investigator collects historic data (demographic and clinical characteristics) from medical records if available, or else by interviewing the patient. Likewise, the investigator collects treatment related data during initial visit and follow-up visits. The investigator documents the study-relevant data for each patient in the electronic case report form (eCRF). All variables as indicated in **Table 1** are routinely collected during regular office visits. The CRF is available upon request (see Table 2: List of stand-alone documents, Annex 1).

Variables	Initial visit	Follow-up visit 1	Follow-up visit 2	Follow-up visit 3	Final visit
Demography	Х				
Employment status	Х	X	Х	X	Х
Education	Х				
Smoking	Х	X	Х	X	Х
Vitamin D intake	Х	Х	Х	X	Х
Other vitamin or nutrient intake	Х	Х	Х	X	Х
Medical history	Х				
Specific MS history	Х	X	Х	X	Х
Concomitant medication	Х	X	Х	X	Х
Concomitant diseases	Х	Х	Х	X	Х
Disease course		X	Х	X	Х
Expanded Disability Status Scale	Х	X	Х	X	X
Local skin reactions	Х	X	Х	Х	Х

Table 1: Tabulated overview on variables collected during the study

			-		
Expected/true treatment days	Х	X	X	Х	Х
Symbol Digit Modalities Test (SDMT)	Х		X		X
Participation in the BETAPLUS ® nurse support program	Х	X	X	Х	X
Participation in the PTMS program	Х	X	X	Х	X
Satisfaction with current way of Betaferon ® injection	Х	X	Х	Х	X
Injection site pain with current way of Betaferon ® injection	Х	X	X	Х	X
Flu-like symptoms following application of Betaferon ®	Х	X	Х	Х	X
Prophylactic analgesic use prior to Betaferon ® injection with current way of injection	Х	X	X	Х	X
Using electronic features of BETACONNECT TM	Х	X	X	Х	X
CES-D questionnaire (depression)	Х	Х	X	Х	Х
SF-36 questionnaire (HrQoL)	Х	X	X	Х	X
EQ-5D (utilities)	Х				Х
WEIMuS questionnaire (fatigue)	Х	Х	X	Х	Х
MSSM-R questionnaire (self- management)	Х	X	X	Х	X
CMSS questionnaire (coping)*	Х	X	X	Х	X
ISU-DYA Inventory (social support)*	Х	X	X	Х	X
Adverse Events		X	X	Х	Х
Medical Device related events and PTCs (including use errors)		X	X	Х	X
Reason for end of observation					Х

\*only for patients in centers, where the PTMS program is offered

